6.1.3.2 Dosing with single capsule (140 μg) tropifexor supply

After tropifexor and matching placebo is replaced by the 140 μ g hard gelatin single capsule, in order to maintain the blind, placebo capsules matching tropifexor 140 μ g and placebo tablets matching licogliflozin (LIK066) 10 mg will be given to participants as indicated in Table 6-6, so that all participants will receive 1 capsule and 3 tablets per day. **One capsule from the bottle**, and **3 tablets from the blister pack** should be taken close to the evening meal; either just prior to (within 5 minutes) consuming the evening meal, or no more than 30 minutes after consuming the evening meal and at about the same time each day.

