6.7.2 Instruction for prescribing and taking study treatment

Participants should be instructed to take the dose of study medication daily, close to the evening meal; either just prior to (within 5 minutes) consuming the evening meal, or no more than 30 minutes after consuming the evening meal and at about the same time each day. Only at Baseline and week 4 visit, the participants should take their doses at the clinic following a meal instead of in the evening.

Once the protocol amendment v02 is approved and after the tropifexor (LJN452) 10, 30 and 100 μ g and matching placebo hard gelatin capsule supply is depleted, the participant will receive 9 blister packs in a box (10 mg licogliflozin or matching placebo tablets) and 1 bottle of 140 μ g hard gelatin capsules (replacing the 10, 30 and 100 μ g tropifexor or matching placebo capsules) for each 4 week period every 4 weeks through Week 20. At the Week 24, Week 32 and Week 40 visits 2 sets of 4 week supplies of study medication will be distributed to accommodate the 8 weekly visit schedule (Table 8-1). The participants will take **3 tablets** from the blister pack and **1 capsule** from the bottle daily as described above.

If the COVID-19 or other pandemic prevents on-site visits the site may arrange delivery of study medication to a participant's home.

Novartis Amended Protocol Version 02 (Clean) Confidential

6.7.2.1 Overview of treatment - type and number of capsules and tablets taken per day

The 140 μ g dose of tropifexor and its matching placebo are each available as a single hard gelatin capsule. Participants on the study at the time of availability of the single tropifexor/placebo capsule, may continue on the 3-capsule tropifexor (100 μ g + 30 μ g + 10 μ g) or matching placebo regimen, as shown in Table 6-5, until the available 3 capsule supply is depleted.

	·····				······································			
Treatme nt Arm	Tropifexor (LJN452) 10µg capsu le	Tropifexor (LJN452) 30µg capsu le	Tropifexor (LJN452) 100µg capsule	Tropifexor (LJN452) Placebo capsule	Licogliflozi n (LIK066) 10mg table t	Licogliflozi n (LIK066) Placebo tablet	Frequency	
Arm A	1	1	1	0	3	0	Daily	
Combo Tropifexor (L JN452) 140 µg								
& Licogliflozin (LIK066)								
30 mg								
Arm B	1	1	1	0	0	3	Daily	
Mono Tropifexor (L JN452) 140 µg								
Arm C	0	0	0	3	3	0	Daily	
Mono Licogliflozin (LIK066) 30 mg								
Arm D	0	0	0	3	0	3	Daily	
Placebo								

Table 6-5Dosing with 3 capsule (10 + 30 + 100 µg) tropifexor supply

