
After the 3-capsule supply is depleted, participants will take 1-capsule of 140 µg tropifexor or matching placebo daily as described in Table 6-6. No change is made to licogliflozin dosing.

Novartis Amended Protocol Version 02 (Clean) Confidential

Table 6-6	Dosing with single capsule (140 μg) tropifexor supply						
Treatment Arm	Tropifexor (LJN452) 140µg capsule	Tropifexor (LJN452) Placebo capsul e	Licogliflozin (LIK066) 10mg tablet	Licogliflozin (LIK066) Placebo tablet	Frequency		
Arm A Combo Tropifexor (LJN45 2) 140 μg & Licogliflozin (LIK06 6) 30 mg	1	0	3	0	Daily		
Arm B Mono Tropifexor (LJN45 2) 140 μg	1	0	0	3	Daily		
Arm C Mono Licogliflozin (LIK06 6) 30 mg	0	3	3	0	Daily		
Arm D Placebo	0	3	0	3	Daily		

IMPORTANT: Please ensure that the date of the change, and the number of capsules (from 3 capsule to 1 capsule) is accurately captured in the eCRF Change in Dosing log for each participant.

Dosing recommendations:

1. Participants should take 3 Tablets from the blister pack (licogliflozin or matching placebo) & 1 or 3 Capsules (tropifexor or matching placebo) depending on current supply close to the evening meal; either just prior to (within 5 minutes) consuming the evening meal, or no more than 30 minutes after consuming the evening meal, at about the same time each day. Participants directed to take 3 capsules must be reminded that one capsule is to be taken from each of the 3 tropifexor/placebo bottles provided. At Baseline and week 4 the dose will be taken in the morning at the clinic close to a meal instead of in the evening.

Confidential

- 4. Participants should be instructed to swallow the capsules and tablets whole and not to chew them.
- 5. If vomiting or diarrhea occurs during the course of treatment, no re-dosing of the participant is allowed before the next scheduled dose.
- 6. If a dose is missed and not remembered the same day, it should not be made up on a subsequent day.

All kits of study treatment assigned by the IRT will be recorded/databased in the IRT system.

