The investigator must promote compliance by instructing the participant to take the study treatment exactly as prescribed and by stating that compliance is necessary for the participant's safety and the validity of the study. It should be emphasized to the participant that the contents of the study medication bottles are not identical; the participant must take one capsule from EACH bottle and 3 tablets from the blister pack each day. The participant must also be instructed to contact the investigator if for any reason he/she has not taken the study treatment as prescribed.

At site dosing – Baseline and Week 4:

- Participants should take study drug either just prior to (within 5 minutes) consuming the morning meal, or no more than 30 minutes after consuming the morning meal.
- Participants should be instructed to swallow whole capsules and not to chew or open them.
- If vomiting occurs during the course of treatment, participants should not take the study treatment again before the next scheduled dose.
- No evening dose should be taken on the days of the Baseline and Week 4 visits as the daily dose is taken at the site on those 2 days.

Novartis	Confidential	Page 90 of 160
Amended Protocol Version 02 (Clean)		Protocol No. CLJN452D12201C

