HIV antigen/antibody tests	х																
Liver function tests	х	Х	Х	Х	Х	Х	Х	Х	Х	Х	Х	Х	Х	Х	х		

Novartis Amended Protoco		2 (Cloan)				С	Confider	ntial					Dr	F otocol No. CLJI	Page 95 of 160
Period	1	ening	Treatment										EOS/PSW		
Visit Name	Screening 1	Screening 2	Baseline	W2	W4	W8	W12	W16	W20	W24	W32	W40	W48	Unscheduled	Follow-Up W52
Visit Number	1	2	3	4	5	6	7	8	9	10	11	12	13	-	14
Days	-70 to -42	-42 to -1	0	14	28	56	84	112	140	168	224	280	336	-	364
Weeks	-10 to -6	-6 to 0	0	2	4	8	12	16	20	24	32	40	48	0	52
Hematology	Х		Х	Х	Х	Х	Х	Х	Х	Х	Х	Х	Х	Х	х
Clinical Chemistry ⁷	х		Х	Х	Х	Х	Х	Х	Х	Х	Х	Х	Х	х	х
Fasting lipid panel	Х		Х	Х	Х	Х	Х	Х	Х	Х	Х	Х	Х	X	х
Coagulation panel ⁸	х	Х	Х	Х	Х	Х	Х	Х	Х	Х	Х	Х	Х	х	х
Amylase & lipase ⁹	Х		Х								Х				
Serum BUN,creatinine and eGFR (MDRD)	х		х	х	x	х	x	x	x	х	x	x	x		х
Urinalysis (central) ¹⁰	x	x	х	х	х	х	х	х	х	Х	х	х	х		x
Pregnancy and assessments of fertility	s	s	S	S	s	S	s	s	s	S	S	S	S	S	S
Pregnancy Urine dipstick test (local) ¹¹	s	s	S		s	S	S	s	S	S	S	S	S	S	S
Pregnancy serum test (central lab) ¹²	х	х								Х					

lovartis Amended Protocol	Version 02	(Clean)	Confidential										Dr	F otocol No. CLJN	Page 96 of 16
Period	Scree			Treatment										EOS/PSW	
		Screening 2	Baseline	W2	W4	W8	W12			W24	W32	W40	W48	Unscheduled	Follow-Up W52
Visit Number	1	2	3	4	5	6	7	8	9	10	11	12	13	-	14
Days	-70 to -42	-42 to -1	0	14	28	56	84	112	140	168	224	280	336	-	364
Weeks	-10 to -6	-6 to 0	0	2	4	8	12	16	20	24	32	40	48	0	52
Follicle stimulating normone (FSH)	х														

Novartis Amended Protocol	Version 0	Confidential											F ptocol No. CLJI	Page 97 of 160	
Period		ening		Treatment											EOS/PSW
Visit Name	Screening 1	Screening 2	Baseline	W2	W4	W8	W12	W16	W20	W24	W32	W40	W48	Unscheduled	Follow-Up W52
Visit Number	1	2	3	4	5	6	7	8	9	10	11	12	13	-	14
Days			0	14	28	56	84	112	140	168	224	280	336	-	364
Weeks	-10 to -6	-6 to 0	0	2	4	8	12	16	20	24	32	40	48	0	52
Urine screening for drug abuse	х		х												
Drug dispensation			S		S	S	S	S	S	S	S	S			
Drug administration record			х	х	x	х	х	x	x	х	х	х			
Drug Compliance				Х	Х	Х	Х	х	Х	Х	Х	Х			
Participant diary review				S	S	S	s	S	S	S	S	S	S		S
Adverse Events ¹⁸									Х						
Serious Adverse Events ¹⁹	x														
Diet Compliance and exercise counseling			Х	Х	Х	Х	Х	X	Х	Х	Х	Х	Х		х

Novartis				Confidential											Page 98 of 160
Amended Protoco		, ,	l .											otocol No. CLJ	
Period	Scre	ening			r		T	reatme	ent	1	1		1	_	EOS/PSW

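### The counselling sentence in Protocol 6.7.2.1 (one capsule from every bottle) is not limited to the 3-capsule supply and is wrong for participants on the single 140 µg capsule

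*Protocol*

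**What the plan says.** Two tropifexor supplies are in use under Amendment 02. Participants may stay on three capsules (10, 30 and 100 µg) until that stock runs out, then move to one 140 µg capsule or its placebo.

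- **Section 6.1.3.1** gives the one-from-each-of-three-bottles rule under a heading for the 3-capsule supply.
- **Section 6.1.3.2**, for the single capsule, directs one capsule from the bottle, "so that all participants will receive 1 capsule and 3 tablets per day".
- **Section 6.7.2** supplies one bottle of 140 µg capsules "for each 4 week period every 4 weeks through Week 20". It then says: "At the Week 24, Week 32 and Week 40 visits 2 sets of 4 week supplies of study medication will be distributed". The next sentence gives the daily dose as 3 tablets and 1 capsule "from the bottle daily as described above".
- **Section 6.7.2.1**, item 1 of the dosing recommendations, makes the capsule count 1 or 3, "depending on current supply close to the evening meal". It restricts the bottle reminder: "Participants directed to take 3 capsules must be reminded that one capsule is to be taken from each of the 3 tropifexor/placebo bottles provided".
- **Section 6.7.2.1**, the compliance paragraph after that list, has the investigator emphasise that the "contents of the study medication bottles are not identical; the participant must take one capsule from EACH bottle". No supply condition is attached.

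**The concern.** The compliance paragraph describes the three-bottle regimen and appears not to have been adjusted when the single capsule came in. As written it applies to every participant, and for those on the single capsule it conflicts with the other dosing text.

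This is an instruction that sites are told to stress, so it is likely to be repeated to participants. Followed literally by someone holding two 140 µg bottles, it doubles the tropifexor dose. Section 1.1.3 gives 200 µg as the highest daily dose under test in NASH and reports dose-dependent pruritus, dose-related LDL-C increases and dose-related HDL-C decreases. The single doses up to 1000 µg in healthy volunteers, described in the same section, are not repeat-dose evidence. The stake is participant safety and treatment fidelity; the statistical design is not touched.

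**Working it through.** The plan gives no figure to reproduce. The check compares the dosing texts and counts bottles and capsules.

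**Inputs**

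- Dispensing visits, from the "Drug dispensation" row of Table 8-1: Baseline and Weeks 4, 8, 12, 16, 20, 24, 32 and 40, which is 9 visits.
- Sets per visit for the single-capsule supply, from Section 6.7.2: one set through Week 20, two sets at Weeks 24, 32 and 40. One set contains one tropifexor or placebo bottle.
- Prescribed dose on that supply, from Sections 6.1.3.2, 6.7.2 and 6.7.2.1: 1 capsule, 140 µg/day in the active arms.
- Arm sizes, from Section 6.1.3: Arm A 140 and Arm B 80, of 380.

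**Formula.** Literal daily dose = bottles held × 1 capsule per bottle × capsule strength. It assumes that the bottles held are those from the latest dispensing visit.

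| Supply and visits | Bottles held | Contents differ? | Literal daily dose | Prescribed |
|---|---|---|---|---|
| 3-capsule, one set | 3 | Yes | 10 + 30 + 100 = 140 µg | 140 µg |
| Single capsule, Baseline to Week 20 (6 of 9 visits) | 1 | Not applicable | 1 × 140 = 140 µg | 140 µg |
| Single capsule, Weeks 24, 32, 40 (3 of 9 visits) | 2 | No | 2 × 140 = 280 µg | 140 µg |

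**Reading the rows**

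1. For the 3-capsule supply with one set open, the sentence is correct in both its parts.
2. For the single capsule through Week 20, the count is right by coincidence. The remark about differing contents has nothing to refer to.
3. For the single capsule from Week 24, both parts fail. The bottles hold the same product, and one from each gives 280/140 = 2.0 times the planned dose. Against the NASH maximum in Section 1.1.3 this is 280/200 = 1.4 times. In Arms C and D the extra capsule is placebo.

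**Upper bound on exposure.** Arms A and B together: 140 + 80 = 220, and 220/380 = 58%. Only those on the single capsule at some point in Weeks 24 to 48 could be affected. The documents do not give that number.

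**Comparison case.** If two 3-capsule sets are dispensed the same way (an assumption) and both are opened, the literal dose is 2 × (10 + 30 + 100) = 280 µg/day. Opening two sets at once is therefore a hazard on either supply. What is specific to the single capsule is that the sentence is factually wrong.

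**The case against.** The case for treating this as harmless has four parts.

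1. **The sentence limits itself.** It tells people to take one from each bottle because the contents differ. Only the 10, 30 and 100 µg bottles meet that premise, so a double dose means following the second half while ignoring the first.
2. **The right dose is stated repeatedly.** Sections 6.1.1, 6.1.3, 6.1.3.2, 6.7.2 and 6.7.2.1 all give one 140 µg capsule a day. Section 6.7.2 does so directly after the two-set rule. Table 6-6 shows one active capsule for Arms A and B.
3. **The hazard comes from two-set dispensing.** It exists for both supplies. Whether participants are told to open one set at a time cannot be judged here, because dosing items 2 and 3, the label and the diary are not in the public copy.
4. **Controls would catch it.** If each bottle holds just 4 weeks of capsules, taking from two at once uses 8 weeks of supply in 8/2 = 4 weeks. Section 6.6.1 requires pill counts at each visit and a diary. Section 6.7.2.1 requires the participant to contact the investigator if treatment was not taken as prescribed.

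All four points have force. The first two show that the intent can be recovered, so no dose is missing. The third is why 280 µg is a literal-reading figure and not a forecast. The fourth limits duration and harm. None of them makes the sentence true for the single-capsule supply, and the protocol limits the same reminder correctly in two other places. The surrounding text is also not fully clean. Table 6-6 lists 3 placebo capsules for Arms C and D under the single-capsule supply, against the 1 capsule for everyone in Section 6.1.3.2. That is a separate error, but it means a blinded site checking the table finds two different counts.

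**Conclusion.** The concern holds. The compliance sentence in Section 6.7.2.1 contradicts the single-capsule instructions in Sections 6.1.3.2, 6.7.2 and 6.7.2.1, and it should be corrected.

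The dose conflict is confined to supplies dispensed at 3 of 9 visits. There the literal reading gives 280 µg/day in place of 140 µg in Arms A and B. At the other 6 visits the count is right and only the remark about contents misfits. The 220 participants are a ceiling, not an estimate. How often anyone would follow the literal reading is unknown, and capsules per bottle are not stated, so the length of any overdose cannot be calculated. The grade of should-fix rests on a stressed dosing instruction being wrong as written and cheap to correct. No hypothesis test, error rate or sample-size figure changes.

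**What to change.** Limit the sentence to participants on the 3-capsule supply, who take one capsule from each of the three bottles of the set in use. Add that participants on the single-capsule supply take one capsule a day in total, from one bottle.

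Separately, confirm that the dosing items, label or diary tell participants on either supply to use one set at a time, and add this only if it is absent.

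The cost is one protocol sentence and a short note to sites. No visits, tests or participants are added. With the change, the literal dose on the single-capsule supply is 1 × 140 = 140 µg/day at every visit, in line with the text of Sections 6.1.3.2 and 6.7.2.

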6.7.2.2 Dietary restrictions

No food or alcohol should be consumed for 8 hours before each study visit where blood samples will be collected to ensure these laboratory assessments to be taken in a fasted state.

In case of development of diarrhea, a low carbohydrate meal (i.e. \leq 50%) close to taking study medication may help to improve the symptom.

To keep the fat intake as constant as possible, participants participating in this study will be instructed to carefully adhere to American Heart Association (AHA) diet or local equivalent if there is a country specific recommended diet, see Section 16.5. Participants will be asked about dietary compliance to the AHA diet (or local equivalent) as outlined in Table 8-1. Participants should also be counseled regarding appropriate exercise as per local standards. Any significant changes to diet or exercise habits should be reported to the investigator.

7 Informed consent procedures

Eligible participants may only be included in the study after providing (witnessed, where required by law or regulation), Institution Review Board (IRB)/Independent Ethics Committee (IEC) approved informed consent.

If applicable, in cases where the participant's representative(s) gives consent (if allowed according to local requirements), the participant must be informed about the study to the extent possible given his/her level of understanding. If the participant is capable of doing so, he/she must indicate agreement by personally signing and dating the written informed consent form.

Informed consent must be obtained before conducting any study-specific procedures (e.g. all of the procedures described in the protocol). The process of obtaining informed consent must be documented in the participant source documents.

Novartis will provide to investigators in a separate document a proposed informed consent form that complies with the International Council of Harmonization Good Clinical Practice (ICH – E6 GCP) guidelines and regulatory requirements and is considered appropriate for this study. Any changes to the proposed consent form suggested by the investigator must be agreed by Novartis before submission to the IRB/ IEC.

Information about common side effects already known about the investigational treatments can be found in the IBs for tropifexor and licogliflozin. This information will be included in the participant informed consent and should be discussed with the participant during the study as needed. Any new information regarding the safety profile of the investigational drug that is identified between IB updates will be communicated as appropriate, for example, via an investigator notification or an aggregate safety finding. New information might require an update to the informed consent and then must be discussed with the participant.

The following informed consents are included in this study:

- Optional study specific pre-screening consent for pre-screening assessments
- Main study consent, which also includes:

Novartis	Confidential	Page 91 of 160
Amended Protocol Version 02 (Clean)		Protocol No. CLJN452D12201C
• As applicable Pregnancy Outcon	nes Reporting Consent	for female participants or

• As applicable, Pregnancy Outcomes Reporting Consent for female participants or the female partners of any male participants who took study treatment.

Women of child bearing potential must be informed that taking the study treatment may involve unknown risks to the fetus if pregnancy were to occur during the study and agree that in order to participate in the study they must adhere to the contraception requirements for the duration of the study.

Male participants must be informed that if a female partner becomes pregnant while he is enrolled in the study, contact with the female partner will be attempted by site to request her consent to collect pregnancy outcome information.

A copy of the approved version of all consent forms must be provided to Novartis after IRB/IEC approval.

8 Visit schedule and assessments

Assessment schedule (Table 8-1) lists all of the assessments when they are performed. All data obtained from these assessments must be supported in the participant's source documentation.

Participants should be seen for all visits/assessments as outlined in the assessment schedule (Table 8-1) or as close to the designated day/time as possible. Missed or rescheduled visits should not lead to automatic discontinuation. The date of each scheduled visit is calculated with the appropriate interval from the date of the Baseline/randomization visit, not from the date of the previous visit. If a scheduled visit is late by more than half of the planned interval between it and the next scheduled visit, the visit should be skipped.

If the COVID-19 or any other pandemic limits or prevents on-site study visits, alternative methods of providing continuing care may be implemented. Phone calls, virtual contacts (e.g. teleconsulting) or visits by site staff/home nursing service at the participants home depending on local regulations and capabilities, may be considered. In-home visits would be conducted by the site staff (under the responsibility of the investigator), or by a health care provider (HCP) supporting this activity if this is in agreement with the investigator.

Participants who discontinue from study treatment for any reason (see Section 9.1 for more details) should be scheduled for an end of treatment visit as soon as possible, and attend the follow-up visits as indicated in the Assessment Schedule.

Novartis	
Amended Protocol Version 02 (Clean)

Confidential

Participants who discontinue from study or withdraw their consent/oppose the use of their data/biological samples should be scheduled for a final evaluation visit if they agree, as soon as possible, at which time all of the assessments listed for the final visit will be performed. At this final visit, all dispensed investigational product should be reconciled, and any adverse event and concomitant medications not previously reported must be recorded on the electronic case report form (eCRF).

The "X" in the table denotes the assessments to be recorded in the clinical database or received electronically from a vendor. The "S" in the table denotes the assessments that are only in the participant's source documentation and do not need to be recorded in the clinical database.

As per Section 4.6, during a public health emergency as declared by Local or Regional authorities, i.e; pandemic, epidemic or natural disaster that limits or prevents on-site study visits, alternative methods of providing continuing care may be implemented by the investigator as the situation dictates. If permitted by a Local Health authority and depending on operational capabilities, phone calls, virtual contacts (e.g., tele consult) or visits by site staff/ home nursing staff to the participant's home, can replace on-site study visits, for the duration of the disruption until it is safe for the participant to visit the site again.

Novartis	
Amended Protocol Version 02 (Clean)	

Confidential

Page **93** of **160** Protocol No. CLJN452D12201C

Table 8-1Assessment Schedule

Period	Scre	ening		Treatment											EOS/PSW
Visit Name	Screening 1	Screening 2	Baseline	W2	W4	W8	W12	W16	W20	W24	W32	W40	W48	Unscheduled	Follow-Up W52
Visit Number	1	2	3	4	5	6	7	8	9	10	11	12	13	-	14
Days	-70 to -42	-42 to -1	0	14	28	56	84	112	140	168	224	280	336	-	364
Weeks	-10 to -6	-6 to 0	0	2	4	8	12	16	20	24	32	40	48	0	52
Informed consent	Х														
Inclusion / Exclusion criteria	Х	х	х												
Demography	Х														
Medical history/current medical conditions	Х	Х	Х												
Protocol solicited medical history	х	х	х												
Randomization			Х												
Contact IRT	Х	Х	Х		Х	Х	Х	Х	Х	Х	Х	Х	Х	Х	Х
Physical Examination	S	S	S	S	s	S	S	s	S	S	S	S	S	S	S
Vital Signs ¹	Х	Х	х	Х	Х	Х	Х	Х	Х	Х	Х	Х	Х	Х	Х
Body Height	Х														
Body Weight	Х	Х	Х	Х	Х	Х	Х	Х	Х	Х	Х	Х	Х	Х	Х

Novartis			Confidential											Page 94 of 160			
Amended Protoco	I Version 02	2 (Clean)											Pro	otocol No. CLJ	452D12201C		
Period	Scre	ening				r	T	reatme	nt						EOS/PSW		
Visit Name	Screening 1	Screening 2	Baseline	W2	W4	W8	W12	W16	W20	W24	W32	W40	W48	Unscheduled	Follow-Up W52		
Visit Number	1	2	3	4	5	6	7	8	9	10	11	12	13	-	14		
Days	-70 to -42	-42 to -1	0	14	28	56	84	112	140	168	224	280	336	-	364		
Weeks	-10 to -6	-6 to 0	0	2	4	8	12	16	20	24	32	40	48	0	52		
Waist circumference	х	x	х				x			Х			х		Х		
Hip circumference	Х	Х	Х				х			Х			Х		Х		
Prior and ongoing / concomitant medications and non-drug therapies	х	x	х	х	x	х	x	x	х	х	x	х	x	х	х		
Alcohol history / compliance with protocol	х	х	х	х	х	х	x	x	х	Х	х	х	х	х	х		
Smoking history	Х																
Electrocardiogram (ECG) ²	х						x			Х			x				
Liver Biopsy ⁵		Х											Х				
Hepatitis serology ⁶	Х																
HIV antigen/antibody tests	х																
Liver function tests	х	Х	Х	Х	Х	Х	Х	Х	Х	Х	Х	Х	Х	Х	х		

Novartis Amended Protoco		2 (Cloan)				С	Confider	ntial					Dr	F otocol No. CLJI	Page 95 of 160
Period	1	ening	Treatment										EOS/PSW		
Visit Name	Screening 1	Screening 2	Baseline	W2	W4	W8	W12	W16	W20	W24	W32	W40	W48	Unscheduled	Follow-Up W52
Visit Number	1	2	3	4	5	6	7	8	9	10	11	12	13	-	14
Days	-70 to -42	-42 to -1	0	14	28	56	84	112	140	168	224	280	336	-	364
Weeks	-10 to -6	-6 to 0	0	2	4	8	12	16	20	24	32	40	48	0	52
Hematology	Х		Х	Х	Х	Х	Х	Х	Х	Х	Х	Х	Х	Х	х
Clinical Chemistry ⁷	х		Х	Х	Х	Х	Х	Х	Х	Х	Х	Х	Х	х	х
Fasting lipid panel	Х		Х	Х	Х	Х	Х	Х	Х	Х	Х	Х	Х	X	х
Coagulation panel ⁸	х	Х	Х	Х	Х	Х	Х	Х	Х	Х	Х	Х	Х	х	х
Amylase & lipase ⁹	Х		Х								Х				
Serum BUN,creatinine and eGFR (MDRD)	х		х	х	x	х	x	x	x	х	x	x	x		х
Urinalysis (central) ¹⁰	x	x	х	х	х	х	х	х	х	Х	х	х	х		x
Pregnancy and assessments of fertility	s	s	S	S	s	S	s	s	s	S	S	S	S	S	S
Pregnancy Urine dipstick test (local) ¹¹	s	s	S		s	S	S	s	S	S	S	S	S	S	S
Pregnancy serum test (central lab) ¹²	х	х								Х					

lovartis Amended Protocol	Version 02	(Clean)	Confidential										Dr	F otocol No. CLJN	Page 96 of 16
Period	Scree			Treatment										EOS/PSW	
		Screening 2	Baseline	W2	W4	W8	W12			W24	W32	W40	W48	Unscheduled	Follow-Up W52
Visit Number	1	2	3	4	5	6	7	8	9	10	11	12	13	-	14
Days	-70 to -42	-42 to -1	0	14	28	56	84	112	140	168	224	280	336	-	364
Weeks	-10 to -6	-6 to 0	0	2	4	8	12	16	20	24	32	40	48	0	52
Follicle stimulating normone (FSH)	х														

Novartis Amended Protocol	Version 0	Confidential											F ptocol No. CLJI	Page 97 of 160	
Period		ening		Treatment											EOS/PSW
Visit Name	Screening 1	Screening 2	Baseline	W2	W4	W8	W12	W16	W20	W24	W32	W40	W48	Unscheduled	Follow-Up W52
Visit Number	1	2	3	4	5	6	7	8	9	10	11	12	13	-	14
Days			0	14	28	56	84	112	140	168	224	280	336	-	364
Weeks	-10 to -6	-6 to 0	0	2	4	8	12	16	20	24	32	40	48	0	52
Urine screening for drug abuse	х		х												
Drug dispensation			S		S	S	S	S	S	S	S	S			
Drug administration record			х	х	x	х	х	x	x	х	х	х			
Drug Compliance				Х	Х	Х	Х	х	Х	Х	Х	Х			
Participant diary review				S	S	S	s	S	S	S	S	S	S		S
Adverse Events ¹⁸									Х						
Serious Adverse Events ¹⁹	x														
Diet Compliance and exercise counseling			Х	Х	Х	Х	Х	X	Х	Х	Х	Х	Х		х

Novartis				Confidential											Page 98 of 160
Amended Protoco		, ,	l .											otocol No. CLJ	
Period	Scre	ening			r		T	reatme	ent	1	1		1	_	EOS/PSW
Visit Name	Screening 1	Screening 2	Baseline	W2	W4	W8	W12	W16	W20	W24	W32	W40	W48	Unscheduled	Follow-Up W52
Visit Number	1	2	3	4	5	6	7	8	9	10	11	12	13	-	14
Days	-70 to -42	-42 to -1	0	14	28	56	84	112	140	168	224	280	336	-	364
Weeks	-10 to -6	-6 to 0	0	2	4	8	12	16	20	24	32	40	48	0	52
Study treatment completion information ²¹													x		
Study completion information															х

^X Assessment to be carried out at respective visit and data for assessment to be recorded in the source, clinical database or received electronically from a vendor
 ^S Assessment to be carried out and data for assessment to be recorded in the source documentation at the site only
 ¹ Vital signs (including blood pressure and pulse measurements)
 ² For any ECGs with safety concerns, two additional ECG must be performed to confirm the safety finding.

ſ

Novartis	Confidential
Amended Protocol Version 02 (Clean)	

° Biopsy

a). The liver biopsy can be performed any time during the 10 week screening period, and should only be performed in participants who fulfill Screening visit 1 eligibility criteria refer Section 8.3.1.8 for details.

b) Screening biopsy results confirming eligibility are required prior randomization. Plan for the biopsy visit accordingly. The Screening visit 2 assessment can be performed before the biopsy results are obtained.

c). Read by a central pathologist.

d). Week 48 biopsy optional if participant discontinues before 24 weeks treatment period.

⁶ Hepatitis B surface antigen (HBsAg); HCV antibody (Ab) – if detected, reflex to Hepatitis C RNA by PCR; Immunoglobulin M (IgM) Hepatitis A antibodies (IgM anti-HAV) see Section 8.4.2.6.

⁷ At screening visit 1 this also includes ferritin, transferrin saturation, iron, and if not historically available also Anti-nuclear antibodies (ANA), Anti-smooth muscle antibodies (ASMA) and Anti-mitochondrial antibodies (AMA), see Section 8.4.2.2

⁸ Coagulation parameters including APTT, PT, INR and TT and fibrinogen.

⁹ Amylase & lipase to be analyzed at screening & Baseline and subsequently if pancreatitis is suspected.

¹⁰ Dipstick measurements for color, clarity, specific gravity, pH, bilirubin, nitrite, ketones, protein, glucose, blood, urobilinogen and leukocyte esterase will be performed. If dipstick measurement results are positive (abnormal), microscopy would be assessed.

¹¹ Women Of Child Bearing potential (WOCBP) must have a urine dipstick pregnancy test every 4 weeks, including at week 28, 36 and 44 (when there are no study visits), up to and including the follow up visit.

¹² After Baseline visit onwards serum sample to be collected for serum pregnancy test only if urine dipstick test is positive – During the study if test is positive, the participant must be discontinued from study drug.

¹⁷ At Baseline and week 4, to be collected at least 1-2 hours post dose at clinic.

¹⁸ Update as necessary

¹⁹ Update as necessary - SAEs must be reported & recorded until 30 days after the participant has stopped study participation; see appropriate protocol Section 10.1.2.

²¹ For participants who discontinue study treatment prematurely before the end of the treatment period for any reason other than withdrawal of informed consent, the Week 48, End of Treatment (EOT) and Week 52 End of Study (EOS) visits must be performed.

